## 9.9. Investigator Site Adverse Event Reporting Requirements

Classification of an event as serious or non-serious (see [Section 9.1](#)) determines the reporting procedures to be followed. Investigator site reporting requirements for adverse events are summarized in [Table 6](#).

**Table 6: Investigator Site Reporting Requirements for Adverse Events**

Classification	Reporting Time	Reporting Action
SAE	Within 24 hours	Complete AE and SAE portions of CRF and notify site IRB/IEC, as per local IRB/IEC requirements. If unable to enter event in EDC, call the CRO Pharmacovigilance Unit or fax the back-up paper SAE report form to the CRO Pharmacovigilance Unit, within 24 hours.
	Within 5 calendar days	Provide photocopies or document scan of relevant source documents a (eg, progress notes, nurses' notes, laboratory and diagnostic test results, discharge summaries) as requested by the CRO Pharmacovigilance Unit
	Per CRF submission procedure	Record and submit information on appropriate CRFs (eg, Medical History and Concomitant Medications CRFs)
AESI	Within 24 hours	Complete AE and SAE portions of CRF and notify site IRB/IEC, as per local IRB/IEC requirements. If unable to enter event in EDC, call the CRO Pharmacovigilance Unit or fax the back-up paper SAE report form to the CRO Pharmacovigilance Unit, within 24 hours
	Within 5 calendar days	Provide photocopies of relevant source documents a (eg, progress notes, nurses' notes, laboratory and diagnostic test results, discharge summaries) as requested by the CRO Pharmacovigilance Unit
	Per CRF submission procedure	Record and submit information on appropriate CRFs (eg, Medical History and Concomitant Medications CRFs)
Nonserious	Per CRF submission procedure	Record and submit information on appropriate CRFs (eg, Adverse Events, Medical History and Concomitant Medications CRFs)

a Subject name, address, and other personal identifiers should be redacted from all study documents prior to submission.

**Abbreviations:** AESI = adverse events of special interest; CRF = case report form; IRB/IEC = Institutional Review Board/Independent Ethics Committee; SAE = Serious Adverse Event.

For SAEs, in addition to completing the adverse event portion of the CRF, the SAE portion of the CRF must also be completed. The SAE CRF must be completed within 24 hours of

knowledge of the event. If the site is unable to enter the event in the EDC system within 24 hours, notification to the CRO Pharmacovigilance Unit should be conducted via telephone or fax using the back-up paper SAE report form. Follow up information for the SAE should be entered on the SAE CRF or clearly documented on the back-up paper SAE report form, as applicable, upon receipt, and must also be sent to the site IRB/IEC, as required. If a paper SAE report form is used to report follow up information, then it must be signed by the investigator. The SAE CRF should be signed by the investigator only after the data on the form has been finalized. Any source documents (eg, progress notes, nurses' notes, laboratory and diagnostic test results, discharge summaries) provided to the CRO Pharmacovigilance Unit should be redacted so that the subject's name, address, and other personal identifiers are obscured. Only the subject's study number and initials are to be provided (in regions where the provision of such information is permitted). The information in the adverse event and SAE portions of the CRF must match or be reconciled. Where the same data are collected, the forms must be completed in a consistent manner. For example, the same adverse event term should be used on both forms.

In the rare event that the investigator does not become aware of the occurrence of an SAE immediately (for example, if a subject initially seeks treatment elsewhere), the investigator is to document his/her first awareness of the adverse event and report the event within 24 hours after learning of it.

The PTC Therapeutics Safety Department or assigned designee (such as a CRO) contact information for reporting serious adverse events and adverse events of special interest is provided below and may also be found in the Investigator File and the back-up paper SAE report form.

## **9.10. PTC Therapeutics Adverse Event Reporting Requirements**

As the sponsor of the study, PTC Therapeutics is responsible for reporting certain safety information, particularly SAEs and subject deaths related to participation in the study, to each investigator in an expedited manner. If notification of an adverse event requiring expedited reporting to investigators is received, PTC Therapeutics or its designated representative will contact each investigator site participating in this study by e-mail, fax, and/or overnight mail such that the investigator can promptly notify the site IRB/IEC, as applicable, per their local requirements. The PTC Therapeutics Awareness Date (PTCAD) is the date the regulatory reporting clock begins and the date is considered Day 0. The initial expedited safety report will be provided as required according to local regulations after the earliest date PTC Therapeutics or an agent of PTC Therapeutics (eg, a site monitor) becomes aware of an adverse event (eg, within 7 calendar days for deaths or life-threatening events or within 15 calendar days for other reportable events from the PTCAD).

## **10. WITHDRAWAL OF SUBJECTS**

All subjects who receive ataluren should remain in the study whenever possible. However:

- The subject has the right to withdraw consent and discontinue ataluren at any time.
- If the subject's condition substantially worsens after initiating ataluren, the subject will be carefully evaluated by the investigator in consultation with the PTC Therapeutics medical monitor. The subject will be withdrawn from treatment if continuing would place them at risk.
- Upon consultation with the PTC Therapeutics medical monitor, the investigator may withdraw the subject from ataluren treatment, if, in the investigator's clinical judgment, it is not in the subject's best interest to continue.
- If the subject becomes significantly noncompliant with ataluren administration, study procedures, or study requirements, the subject should be withdrawn, particularly when the circumstances surrounding noncompliance increase risk to the subject or are anticipated to substantially compromise the interpretation of study results.
- The subject will be withdrawn from treatment if he/she is unable to tolerate ataluren.
- If the subject becomes eligible to participate in another ataluren nmCF clinical trial program initiated by PTC Therapeutics, and elects to enroll in said study, they will be withdrawn from this study.
- This study may be discontinued by the relevant regulatory authority and/or PTC Therapeutics at any time.

The date ataluren is discontinued and the reason for discontinuation will be recorded in the source documents and in the CRF. The PTC medical monitor (and designee) should be informed via e-mail of when a subject discontinues ataluren.

When ataluren is discontinued (regardless of the reason), the investigator should encourage that all of the evaluations required at the End of Treatment Visit be performed and that any additional evaluations be completed that may be necessary to ensure that the subject is free of untoward effects. The subject should be encouraged to seek appropriate follow-up for any continuing health problems.

A subject who completes the study through Week 192 (Visit 14-End-of-Treatment/Premature-Discontinuation) and is then lost to follow-up during the follow-up period will not be considered to have prematurely withdrawn.

## **11. STATISTICS AND DATA MANAGEMENT**

### **11.1. Sample Size Calculation for the Primary Endpoint**

The pool of patients potentially eligible for this study is described by the inclusion criteria. The sample size is determined by how many patients satisfy all inclusion/exclusion criteria upon applying for study participation, not by any formal statistical analysis.

## **11.2. Population Definition**

### **11.2.1. As-Treated Population**

The as treated population consists of all subjects who received at least 1 dose of ataluren. This population will be evaluated in the analyses of safety and treatment administration.

### **11.2.2. Intent-to-Treat Population**

The intent-to-treat (ITT) population consists of all subjects who have at least 1 post-baseline efficacy assessment. This population will be evaluated in the analysis of efficacy.

## **11.3. General Statistical Considerations**

By-subject listings will be created for each CRF module. Summary tables for continuous variables will contain the following statistics: n, mean, standard deviation, standard error, 95% confidence intervals (CIs) on the mean, median, minimum, and maximum. Summary tables for categorical variables will include N, n, percentage, and 95% CIs on the percentage. Where applicable, the summary data (mean, standard error) will be presented in graphical form by time of visit.

Unless otherwise specified, all analyses will be 2-sided at the 0.05 level of significance.

## **11.4. Specific Statistical Analyses**

### **11.4.1. Study Conduct and Subject Disposition**

Subjects who prematurely discontinue from the study will be reported. Reasons for screening failures and early discontinuations, reasons for study discontinuation, and time of withdrawal from the study will be described.

### **11.4.2. Baseline Characteristics**

Subject characteristics at entry and in each phase of the study will be summarized in frequency tables and descriptive statistics will be provided for quantitative variables.

### **11.4.3. Study Treatment Administration**

For each subject, ataluren administration will be described, inclusive of duration of therapy, dose modifications, dose delays and omissions, and reasons for any deviations from planned therapy.

### **11.4.4. Use of Concomitant Medication and Supportive Therapy**

Concomitant medications will be coded by means of the World Health Organization Drug Dictionary (WHODRUG) dictionary into Anatomical-Therapeutic-Chemical classification (ATC) codes. Type and timing of specific concomitant medications (and non-drug therapies) will be listed and summarized.

### **11.4.5. Primary Variables**

#### **11.4.5.1. Adverse Events**

Adverse events will be classified using the MedDRA classification system. The severity of adverse events will be graded by the investigator according to the CTCAE, Version 3.0 whenever possible. A treatment-emergent adverse event is defined as an adverse event that occurs or worsens in the period extending from the day of a subject's first ataluren dose in this study to 4 weeks after the last ataluren dose in this study.

The frequency of subjects experiencing a specific adverse event will be tabulated by treatment group, body system, and MedDRA term. In the by-subject analysis, a subject having the same event more than once will be counted only once. Adverse events will be summarized by worst CTCAE grade.

Adverse events classified as CTCAE Grade 3 or higher; study-drug-related events; adrenal, hepatic, and renal events leading to special diagnostic evaluations; events leading to discontinuation from treatment; and SAEs will be considered with special attention.

#### **11.4.5.2. Laboratory Data**

Hematological, serum biochemistry, adrenal assessments, and urine data and their changes (only for continuous laboratory parameters) from baseline will be summarized by visit.

Hematological, serum biochemistry, adrenal assessments, and urine data will be graded according to CTCAE severity grade when applicable. For parameters for which a CTCAE scale does not exist, the frequency of subjects with values below, within, and above the normal ranges will be summarized. Summary tables will be presented for each relevant assay to show the number of subjects by severity grade with corresponding percentages. Subjects will be characterized only once for a given assay, based on their worst severity grade observed during the time period of interest.

Shift tables for hematology, serum biochemistry, adrenal assessments, and urine data will also be presented showing change in CTCAE severity grade from baseline to each visit. For parameters for which a CTCAE scale does not exist, shift tables will be presented showing change in results from baseline (normal, low and high [or abnormal]) to each visit (normal, low and high [or abnormal]).

Separate listings and tables will be created for assessment of adrenal, hepatic, and renal parameters based on the conditions listed in [Section 6.3.1](#).

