markers (protein and blood), and serum electrolytes (Na+, K+, HCO3, Mg2+, Ca2+, and phosphate).

During the Phase 2b double-blind study of ataluren in nmDMD (PTC124-GD-007-DMD), mean total cholesterol and triglycerides were in the upper range of normal at baseline and increased on study, reaching borderline high or high values. Baseline mean cholesterol and triglycerides values were higher in patients receiving systemic corticosteroid therapy. During the treatment period, increases in mean cholesterol levels were observed in patients receiving systemic corticosteroid therapy, more prominently in ataluren-treated patients than in the placebo arm. In patients not receiving systemic corticosteroid therapy, mean cholesterol levels increased similarly across all 3 treatment arms (placebo, 10-, 10-, 20-mg/kg TID, and 20-, 20-, 40-mg/kg TID), and mean triglyceride levels increased minimally in ataluren-treated patients. Similar changes were not seen in the double-blind study for nmCF (Study 009). In that study, low cholesterol levels were observed prior to treatment in >40% of patients across both treatment arms. No ataluren-treated patients shifted from normal cholesterol at baseline to high cholesterol at Week 48. Shifts from normal triglycerides at baseline to high triglycerides at Week 48 were observed in both treatment arms, and were somewhat higher in placebo. Despite the lack of effect of ataluren on total cholesterol and triglycerides in nmCF, total cholesterol and triglycerides will continue to be monitored throughout this study.

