2.4. Sample Size

Approximately 70 patients that completed participation in Study 009 will be enrolled into the study. The sample size is not determined by statistical power.

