4.10.2. Clinical Laboratory Evaluations

Hematology laboratory assessments will include white blood cell count with differential, hemoglobin, hematocrit, mean corpuscular volume, mean corpuscular hemoglobin, mean corpuscular hemoglobin concentration, total red cell count with morphology, and platelet count. These parameters will be measured at all study visits.

Biochemistry laboratory assessments will include sodium, potassium, chloride, bicarbonate, blood urea nitrogen, creatinine, magnesium, calcium, phosphorus, uric acid, glucose, total protein, albumin, globulin, albumin:globulin ratio, bilirubin (total, direct and indirect), creatine kinase (CK), lactate dehydrogenase (LDH), alanine aminotransferase (ALT), aspartate aminotransferase (AST), gamma glutamyl transferase (GGT), alkaline phosphatase, total cholesterol, high-density lipoprotein (HDL), low-density lipoprotein (LDL), triglycerides, and cystatin C. These parameters will be measured at all study visits. Ideally, subjects should have fasted for at least 8 hours prior to blood collection.

Urinalysis assessments will include pH, specific gravity, glucose, ketones, blood, protein, creatinine, urobilinogen, bilirubin, nitrite, and leukocyte esterase. These parameters will be measured at all study visits.

Hematology, serum biochemistry, and urinalysis data and their changes from baseline (only for continuous laboratory parameters) will be summarized by visit. Maximal and minimal change from baseline in each parameter will also be summarized.

Shift tables for hematology, serum biochemistry, and urinalysis will also be presented showing change in CTCAE severity grade from baseline to each visit. For parameters for which a CTCAE scale does not exist, shift tables will be presented showing change in results from baseline (normal, low, and high [or abnormal]) to each visit (normal, low, and high [or abnormal]).

Frequency tables will be presented for safety monitoring parameters to show the number and percentages of subjects by severity grade categories defined in [Table 2](#). If a CTCAE grade does not exist, abnormal results will be summarized by protocol-defined thresholds as noted in [Table 2](#). Subjects will be characterized only once for a given assay, based on their worst severity grade observed during the time period of interest.

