6. ANALYSIS CHANGES FROM PROTOCOL

Due to the premature termination of the study, the time of withdrawal from the study analysis has been removed compared to current protocol version 3.0. The paired t-test on FEV₁ and the summary of FEF₂₅₋₇₅ have also been removed. On the other hand, the drug exposure adjusted incidence rate of TEAEs has been added. Summary of occurrence of TEAE has been added as well.

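### The SAP narrows the once-per-subject worst-grade laboratory table to nine hepatic and renal parameters without declaring it, so for other assays the number of subjects ever abnormal, by worst grade, is not reported

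*Protocol*

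**What the plan says.** **Protocol 11.4.5.2 (Laboratory Data)** sets the scope in four steps.
- Grading: "Hematological, serum biochemistry, adrenal assessments, and urine data will be graded according to CTCAE severity grade when applicable".
- Assays with no CTCAE scale: "the frequency of subjects with values below, within, and above the normal ranges will be summarized".
- Table: "Summary tables will be presented for each relevant assay to show the number of subjects by severity grade with corresponding percentages".
- Counting rule: "Subjects will be characterized only once for a given assay, based on their worst severity grade observed during the time period of interest".

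A later sentence in the same section adds separate listings and tables for adrenal, hepatic and renal parameters.

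**SAP 4.10.2 (Clinical Laboratory Evaluations)** repeats the counting rule but narrows the table: "Frequency tables will be presented for safety monitoring parameters", using the categories of SAP Table 2. An assay without a CTCAE grade is summarized against the Table 2 thresholds. For hematology, biochemistry and urinalysis the SAP keeps by-visit summaries, maximal and minimal change, and shift tables from baseline to each visit by CTCAE grade or by normal/low/high. Adrenal assays are named in none of these summaries.

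**SAP Section 6** lists the removal of the time-of-withdrawal analysis, the FEV1 paired t-test and the FEF25-75 summary, and the addition of exposure-adjusted incidence rates. It ends: "Summary of occurrence of TEAE has been added as well". The laboratory table and the adrenal assays are not mentioned. SAP Section 1 gives the SAP precedence where the two documents conflict.

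**The concern.** The primary endpoint (Protocol 3.2, SAP 2.3.1) is a safety profile that includes the frequency and severity of laboratory abnormalities. In a long-term single-arm study the natural summary is how many subjects ever had an abnormality, and how severe it became. The protocol planned that count broadly; the SAP gives it only for Table 2, and a reader of Section 6 would not learn that anything had changed.

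Some of the assays left out matter to the protocol itself. Protocol 14.1.4 says that "total cholesterol and triglycerides will continue to be monitored throughout this study", and the renal monitoring plan in Protocol 14.2.3.1.2 discusses serum electrolytes by grade. Neither group has a row in Table 2, and neither does any hematology assay. Whether Table 2 is complete as a monitoring tool is a clinical question that I leave aside; the point here is only which assays receive a worst-grade count.

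**Working it through.** The plan offers no figure to reproduce: the study is descriptive, and "The sample size is not determined by statistical power". The check is a comparison of texts, a count, and an illustration.

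**1. Scope side by side**

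| Item | Protocol 11.4.5.2 | SAP 4.10.2 |
|---|---|---|
| Worst-grade table, once per subject | Each relevant assay | Table 2 parameters only |
| Assays without a CTCAE scale | Below/within/above normal | Table 2 thresholds |
| By-visit shift tables | Hematology, biochemistry, adrenal, urine | Hematology, biochemistry, urinalysis |
| Separate adrenal, hepatic and renal tables | Yes, as an additional item | Hepatic and renal, through Table 2 |

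Because the protocol lists the organ-specific tables separately, its general table was not meant to be the monitoring-parameter table alone.

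**2. Assays affected**

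Items named in SAP 4.10.2, with the differential counted with the white cell count and red cell morphology with the red cell count: hematology 8, biochemistry 29, urinalysis 11. Total: 8 + 29 + 11 = 48.

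Table 2 has nine rows: total bilirubin, ALT, AST, GGT, cystatin C, creatinine, BUN, the urine protein:creatinine ratio and urine blood. Counting both parts of the ratio, these draw on 7 serum and 3 urine items, 10 in all. Remaining: 48 − 10 = 38 (79%). None of the 8 hematology items is covered.

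**3. Why by-visit tables do not give the count**

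Let p be the share abnormal at each of k visits, with every subject attending every visit, and E the share ever abnormal at those visits. Then p ≤ E ≤ min(1, k × p). The lower limit applies when the same subjects are abnormal each time, the upper when different subjects are abnormal each time. Independence between visits gives 1 − (1 − p)^k, which lies inside the range and is not its ceiling.

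The schedule has 192/16 = 12 on-treatment laboratory visits after Week 1 (Weeks 16 to 192). SAP 2.1 says the study will be terminated prematurely, so k = 6 is shown as an assumed alternative. The values of p are also assumptions; the documents give none.

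| p | k | Lowest E | Independent visits | Highest E |
|---|---|---|---|---|
| 2% | 12 | 2% | 1 − 0.98^12 = 21.5% | 12 × 2% = 24% |
| 5% | 12 | 5% | 1 − 0.95^12 = 46.0% | 12 × 5% = 60% |
| 2% | 6 | 2% | 1 − 0.98^6 = 11.4% | 6 × 2% = 12% |
| 5% | 6 | 5% | 1 − 0.95^6 = 26.5% | 6 × 5% = 30% |

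The by-visit tables fix E only in special cases, for example when abnormalities occur at no visit or at just one.

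**4. Unscheduled results**

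SAP 5.2 takes analysis visits as the scheduled visits, without window mapping. An abnormality seen only at an unscheduled draw may therefore appear in no by-visit shift table.

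**The case against.** A reader might infer that the frequency of most laboratory abnormalities is never reported. The documents do not support that. SAP 4.10.2 tabulates grade, or normal/low/high, at each visit for all three panels, and SAP 5.2 adds a Final Visit to the by-visit summaries. Frequency and severity over time are reported; only the once-per-subject worst on-study count is missing.

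Other outputs help in part. SAP 4.10.1 counts treatment-emergent adverse events once per subject by worst grade and summarizes laboratory abnormalities reported as such events. But Protocol 9.1.1 keeps abnormalities that need no intervention or further investigation out of adverse event reporting, so those counts are incomplete by design. Maximal and minimal change describes the size of a change, not grade or number of subjects. With about 70 subjects, by-subject listings would let someone rebuild the counts by hand, but a listing is not a planned summary of a primary endpoint.

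Three limits stand.
- The protocol does not define a relevant assay. Urine pH, specific gravity or the albumin:globulin ratio could reasonably be left out, so 38 is an upper count. That would not explain leaving out all hematology, electrolytes and lipids, or the silence in Section 6.
- The adrenal omission has little effect. Protocol 8.2.7.2 draws cortisol, renin and aldosterone at Screening and afterwards only when clinically indicated, so post-baseline tables would be nearly empty. SAP 4.10.1 still tabulates adrenal events leading to special evaluation.
- Monitoring lipids does not by itself require a worst-grade table. Protocol 14.1.4 describes earlier lipid findings largely through mean changes and shifts to Week 48, formats the SAP keeps.

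**Conclusion.** The concern holds as an undeclared narrowing of one descriptive table that bears on the primary endpoint. Up to 38 of 48 named items lose the number and percentage of subjects by worst on-study grade (or low/normal/high), while keeping by-visit shift tables. The missing count cannot in general be derived from what remains. The 2% to 24% and 5% to 60% ranges are illustrations: they rest on assumed per-visit rates, 12 visits and full attendance, and they narrow with fewer visits. They are not estimates for this study.

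Worst-grade counts for the Table 2 hepatic and renal parameters are unaffected. The plan should be corrected, but nothing here suggests that data are lost or that laboratory safety goes unreported.

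**What to change.** In SAP 4.10.2, restore for each hematology, biochemistry and urine assay the number and percentage of subjects by worst post-baseline CTCAE grade, or by low/normal/high where no scale exists. Include unscheduled results and state the period that the table covers. For cortisol, renin and aldosterone, a by-subject listing with normal ranges is enough. If some assays are left out on purpose, name them in Section 6 with the reason.

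The cost is a few standard tables. Scheduled results are already graded for the shift tables, unscheduled results need the same rule applied, and no new data are collected. SAP Section 1 allows such a change by amendment before database lock.
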